11 START AND COMPLETION OF THE STUDY

The start-of-study is defined as the date of the first activated site.

The end-of-study is defined as the date of end of study participation by the last subject in the last country where the study was conducted.

APPENDIX A. STUDY-SPECIFIC ABBREVIATIONS AND TERMS

Abbreviation	Definition

Ab antibody

AD atopic dermatitis

ADerm-IS Atopic Dermatitis Impact Scale

ADerm-SS Atopic Dermatitis Symptom Scale

ADL activities of daily living

AE Adverse event

AESIs AE of special interest

Ag antigen

ALC Absolute lymphocyte count

ALT alanine transaminase

ANC Absolute neutrophil count

AO As Observed

AST aspartate transaminase axSpA axial spondyloarthritis BCG bacilli Calmette-Guérin

BSA body surface area
CD Crohn's disease
CI confidence interval

COVID-19 Coronavirus Disease – 2019

CPK creatine phosphokinase

CRP C-reactive protein
CS Clinically significant

CTCAE Common Terminology Criteria for Adverse Events

CTEP Cancer Treatment Evaluation Program

CXR chest x-ray

CYP3A cytochrome P450 3A

DLQI Dermatology Life Quality Index
DMC data monitoring committee

DNA deoxyribonucleic acid

DTP direct-to-patient

DVT deep vein thrombosis

EASI Eczema Area and Severity Index

EC Ethics Committee
ECG Electrocardiogram

eCRF electronic case report form

EDC Electronic data capture

FAS Full analysis set

FSH follicle-stimulating hormone

GCA giant cell arteritis

GCP Good clinical practice

GFR glomerular filtration rate

GI gastrointestinal

GPSP Good Post-marketing Study Practice

HBV Hepatitis B virus
HCV Hepatitis C virus
HCV Ab HCV antibody

HIV Human immunodeficiency virus

HIV Ab HIV antibody

hsCRP High-sensitivity C Reactive Protein

ICH International Council for Harmonisation of Technical Requirements for Pharmaceuticals

for Human Use

IEC Independent ethics committee

IEC/IRB Independent Ethics Committee/Institutional Review Board

IFN interferon

IGRA Interferon-Gamma Release Assay

IL interleukin

IMP Investigational Medicinal Product
INR International normalized ratio

IRB Institutional review board

IRT Interactive response technology

ITT Intent to Treat

IU International Unit

IUD Intrauterine device

IUS Intrauterine hormone-releasing system

JAK Janus kinase

JAK1 Janus kinase 1
JAK2 Janus kinase 2

MACE major adverse cardiovascular event

MCID minimum clinically important difference

MDA minimal disease activity

MDRD Modification of Diet in Renal Disease

MedDRA Medical Dictionary for Regulatory Activities

mRNA messenger ribonucleic acid

N/A not applicable

NCI National Cancer Institute

NCS Not clinically significant

NMSC non-melanoma skin cancer

NRS Numerical Rating Scale

OR odds ratio

PCR Polymerase chain reaction
PD Premature discontinuation

PD Visit Premature Discontinuation visit

PDE4 phosphodiesterase type 4
PGI Patient Global Impression

PGIS Patient Global Impression of Severity
PGIT Patient Global Impression of Treatment

PK Pharmacokinetic(s)

POEM Patient Oriented Eczema Measure

PPD purified protein derivative

PPE Personal Protective Equipment

PRO patient reported outcomes

PsA psoriatic arthritis
PT preferred term

PUVA psoralen and ultraviolet A

QD once daily
QoL quality of life

QTcF QT interval corrected for heart rate using Fridericia's formula

RA rheumatoid arthritis

RNA ribonucleic acid

ROA Route of Administration

RSI Reference Safety Information

SAE Serious adverse event
SAP Statistical analysis plan
SAR serious adverse reaction

SARS-CoV-2 Severe acute respiratory syndrome coronavirus 2

SC1 Study Cohort 1
SC2 Study Cohort 2
SC3 Study Cohort 3
SC4 Study Cohort 4

SmPC Summary of Product Characteristics

SOC System Organ Class

SS1 Sub-Study 1
SS2 Sub-Study 2

SUSAR Suspected unexpected serious adverse reactions

TA MD Therapeutic Area Medical Director

TA SD Therapeutic Area Scientific Director

TB tuberculosis

TEAEs treatment emergent adverse events

TNF tumor necrosis factor
TYK2 tyrosine kinase 2

ULN upper limit of normal

UV Ultra-violet

vIGA-AD validated Investigator's Global Assessment for AD

WBC white blood cell

APPENDIX C. LIST OF PROTOCOL SIGNATORIES

APPENDIX D. ACTIVITY SCHEDULE

The following table shows the required activities across the Screening and subsequent study visits. The individual activities are described in detail in the **Operations Manual** (Appendix F). Allowed modifications due to COVID-19 are detailed in the Operations Manual.

Study Activities Table

Activity	Screening	Baseline	Week 4	Week 12	Week 16	Week 24	Unscheduled Visit	Premature Discontinuation Visit	30-day Follow Up Visit
	D-35 to D -1	0.1	D 29	D 85	D 113	D 169			
Visit Window (days)			+3	13	±3	13			±3
Subject Information and Informed Consent	✓								
Eligibility criteria	✓	✓							
Medical/Surgical history	✓	✓							
Alcohol, nicotine and drug history	✓								
Prior/concomitant therapy	✓	✓	✓	✓	✓	✓	✓	√	*
TB Risk Assessment Questionnaire	✓								
Patient Reported Outcomes: Worst Pruritus NRS (Handheld device)	✓	✓	✓	✓	✓	✓	✓	✓	
Patient Reported Outcomes: ADerm-SS, ADerm-IS (Baseline on site tablet device and then assessed daily via a handheld ePRO device through Week 24)		*	✓	V	V	V	*	V	
Patient Reported Outcomes:- DLQI, POEM, PGIS, PGIT		✓	✓	✓	✓	✓	✓	√	
Subject hand-held device review (dispense at Screening)	✓	✓	✓	*	*	✓	*	1	
Body Weight	✓	✓	✓	✓	*	✓	*	1	
Vital signs	✓	✓	✓	✓	✓	✓	✓	✓	
Physical exam	✓	✓		✓		✓	✓	1	
12-Lead ECG	✓								

Activity	Screening	Baseline	Week 4	Week 12	Week 16	Week 24	Unscheduled Visit	Premature Discontinuation Visit	30-day Follow Up Visit
	D-35 to D -1	D1	D 29	D 85	D 113	D 169			
Visit Window (days)			+3	+3	+3	±3			+ 3
Chest x-ray for TB Assessment	✓								
Adverse event assessment	√	✓	✓	✓	✓	✓	✓	✓	*
Investigator Assessments (EASI, BSA, vIGA)	✓	✓	✓	✓	✓	✓	*	1	
For China sites only, dispense subject paper diary cards for AE symptoms, concomitant therapy, and investigational product administration as applicable	V	V	✓	V	V	✓			
For China sites only, review AE symptoms and concomitant therapy assessment from the subject paper diary cards		V	V	V	V	✓	1	1	1
For China sites only, collect subject paper diary cards for AE symptoms, concomitant therapy, and investigational product administration		V	✓	V	V	V	1	1	*
Serum pregnancy test (for all subjects of childbearing age)	✓								
Local urine pregnancy test (for all subjects of childbearing age)		✓	✓	✓	✓	✓	✓	✓	✓
Dispense urine pregnancy tests for monthly home testing			✓		✓				
Review and document pregnancy avoidance recommendations (for all subjects of childbearing age)		*	V	V	V	*	*	V	
Beta-D-glucan (Japan only)	✓								
Central Laboratory Tests Clinical Chemistry, Hematology	✓	✓	✓	✓	✓	✓	✓	√	✓
TB Test (QuantiFERON-TB Gold Plus test [or interferon gamma release assay (IGRA) equivalent such as T-SPOT test] and/or local PPD skin test, if required)	1								

Activity	Screening	Baseline	Week 4	Week 12	Week 16	Week 24	Unscheduled Visit	Premature Discontinuation Visit	30-day Follow Up Visit
	D-35 to D -1	D1	D 29	D 85	D 113	D 169			
Visit Window (days)			+3 +3	+3	+3	+3			8 +I
Central Lab- HIV Screening, Hepatitis B and C Screening	✓								
Randomization/Drug assignment		✓		✓					
Dispense Study Drug		✓	✓	✓	✓				
Review and copy investigational product administration information from subject paper diary cards for China sites only			*	✓	V	*	1	*	
Optional biomarker samples: Whole blood DNA		✓							
Optional biomarker samples: Plasma/serum proteomic		✓	✓	✓	✓	✓	✓	*	
Optional biomarker samples: PBMC		✓	✓	✓					
Dispense wearable tool (Substudy Only)	✓								
Subject uses wearable tool for 7 nights prior to Baseline and following Visit (Substudy Only)		✓	✓	V	V				
Collect wearable tool (Substudy Only)						✓		✓	

APPENDIX E. PROTOCOL SUMMARY OF CHANGES

Previous Protocol Versions

Protocol	Date
Version 1.0	08 April 2022
Version 2.0	01 February 2022
Administrative Change 1	05 April 2023

The purpose of this version is to update the protocol regarding EU Clinical Trial Regulation requirements, and to align the protocol with updated safety standards for upadacitinib study protocols.

The following changes were made for Version 3.0 of this protocol:

Protocol

- Applied administrative change and minor text edits as needed.
- Title page: Updated with EU CT number, updated Sponsor/Emergency Medical Contact information.
- Section 1 (Synopsis): Updated to align with version 3.0 revisions.
- Section 2.1 (Background and Rationale): Updated approvals for treatment with upadacitinib.
- Section 2.2 (Benefits and Risks to Subjects): Added AEs that have been observed in patients receiving JAK inhibitors including upadacitinib.
- Section 5.2 (Contraception Recommendations): Updated language for females of childbearing potential, added section on Contraceptive Counseling.
- Section 5.3 (Prohibited Medications and Therapy):
 - Updated list of prohibited biological therapies with immunosuppressive potential.
 - Updated examples of commonly used strong CYP3A inhibitors and inducers.
- Section 5.4 (Prior and Concomitant Therapy):
 - Added language to indicate that subjects should not have received a COVID-19 vaccination in the 7 days prior to randomization or plan to receive a COVID-19 vaccination within the first 7 days after initiation of study drug.
- Section 5.5 (Withdrawal of Subjects and Discontinuation of Study):
 - Updated language indicating that laboratory results or AEs that either meet the criteria for discontinuation of study drug, or rule out safe continuation of the study drug, would be determined by the investigator.
 - Updated malignancy language.
- Added Section 5.11, Publication Policy.
- Section 6.1 (Complaints and Adverse Events):

- Added Malignancy and Hypersensitivity Reactions and corresponding eCRFs.
- Added language for SUSAR reporting in the EU.
- Added Fractures and Retinal detachment to list of AESIs.
- Section 6.2 (Toxicity Management):
 - Updated language for management of serious infections, muscle-related symptoms, thrombosis events, and COVID-19.
 - Updated Elective and Emergency Surgeries to indicate that elective surgery prior to study primary endpoint must be discussed with the TA MD and performed with TA MD approval.
- Section 8.3 (Subject Confidentiality): Added language regarding the documentation of personal data breaches.
- Section 9 (Source Documents and Case Report Form Completion), Section 10 (Data Quality Assurance): Added Regulation [EU] No 536/2014.
- Appendix D (Activity Schedule):
 - To update the study activities table to allow for ADerm-SS and ADerm-IS PROs to be collected at the Baseline visit on the site tablet device).

Operations Manual

- Applied administrative changes and minor text edits as needed.
- Section 1 (Contacts): Updated Sponsor/Emergency Medical Contact information.
- Section 2.1 (Individual Treatment Period Visit Activities):
 - Added review and documentation of compliance with pregnancy avoidance recommendations for females of childbearing potential.
 - Updated Baseline visit with language for Post-Baseline Visits.
- Section 3.4 (Adverse Event Assessment): Updated to specify SAEs as protocol-related.
- Section 3.5 (Patient-Reported Outcomes):
 - Updated to indicate that The PRO instruments to be completed on the site device at scheduled study visits should be done before any interaction with site personnel has occurred (e.g., before drug administration, clinical assessments, and discussion of AEs or any review of laboratory findings) to avoid biasing the subject's response.
 - Updated to indicate that ADerm-SS and ADerm-IS will be administered on electronic handheld devices from **Baseline** through Week 24.
- Section 3.12 (Physical Examinations and Assessments): Updated CXR and Vaccine requirements.
- Section 3.14 (Clinical Laboratory Tests):
 - Updated to indicate that the investigator will record the laboratory result as an adverse
 event if the out-of-range value results in discontinuation of study drug, or necessitates
 therapeutic medical intervention.

- Added QuantiFERON-TB Gold Plus and Varicella antibody tests to Local Laboratory Tests.
- Indicated that results of any HIV antibody testing will be retained by the study site under confidential restrictions.
- Added language for Beta-D Glucan Testing (for Japan only).
- Updated TB testing procedures.
- Updated language for indeterminate QuantiFERON-TB Gold Plus test.
- Section 4.1 (Methods and Timing of Safety Assessment): Added supplemental eCRFs for Malignancy and Hypersensitivity Reactions.
- Section 4.2 (Reporting Adverse Events and Intercurrent Illnesses): updated SUSAR language to specify as in accordance with global and local requirements.

#### 1.0 Introduction

This Statistical Analysis Plan (SAP) describes the statistical analyses for ABT-494 Study M22-000 (Flex-Up) "A Phase 3b/4 Randomized, Blinded, Treat-to-Target and Dose-Flexibility Study of Upadacitinib in Adult Subjects with Moderate to Severe Atopic Dermatitis (Flex-Up)."

This study aims to provide descriptive data on the efficacy and safety of dose escalation to upadacitinib 30 mg once daily (QD) and dose reduction to upadacitinib 15 mg QD based on a clinical response after 12 weeks of treatment. This data will inform the clinical management for subjects with moderate to severe AD treated with both approved doses of upadacitinib.

The analyses of pharmacodynamic biomarker endpoints will not be covered in this SAP.

The SAP will not be updated in case of administrative changes or amendments to the protocol unless the changes impact the analysis.

[figure not shown]
Unless noted otherwise, all analyses will be performed using SAS Version 9.4 (SAS Institute Inc., Cary, NC 27513) or later under the UNIX operating system.

# 2.0 Study Objectives and Design

# 2.1 Study Objectives, Hypotheses and Estimands

The primary study objectives are:

- 1. Sub-Study 1 (SS1): The primary study objective for SS1 is to evaluate the efficacy and safety of dose escalation to upadacitinib 30 mg QD in subjects who do not achieve Eczema Area and Severity Index (EASI) 90 on upadacitinib 15 mg QD after 12 weeks.
- 2. Sub-Study 2 (SS2): The primary study objective for SS2 is to evaluate the efficacy and safety of dose reduction to upadacitinib 15 mg QD in subjects who achieve EASI 90 on upadacitinib 30 mg QD after 12 weeks.

The additional objective is to generate evidence on patient impact (patient reported outcomes [PROs]) with upadacitinib treatment based on a clinical response target (EASI 90) (Treat-to-Target).

No hypothesis testing will be performed in this study.

The estimand corresponding to the primary endpoint is defined as:

• The proportion of subjects who achieve EASI 90 at Week 24, regardless of treatment discontinuation, with upadacitinib treatments (upadacitinib 15 mg or 30 mg QD) in adult subjects with moderate to severe AD.

# 2.2 Study Design Overview

[figure not shown]
This is a Phase 3b/4, randomized, blinded, treat-to-target, dose-flexibility, multi-center study that will evaluate upadacitinib, as monotherapy, in approximately 454 adult subjects ( $\geq 18$  and < 65 years of age) with moderate to severe AD who are candidates for systemic therapy.

The study is comprised of a 35-day Screening Period, a 12-week double-blind period and a 12-week single-blind period. During the single-blind period, subjects will be blinded to the upadacitinib dose and EASI score evaluations.

The study treatment duration will be 24 weeks.

After the last study visit, a 30-day follow-up visit (or phone call if a visit is not possible) will be completed to determine the status of any new or ongoing AEs/SAEs and concomitant medications.

Subjects who meet the eligibility criteria will be randomized in a 1:1 ratio to enter SS1 to receive oral doses of upadacitinib 15 mg QD at Baseline or SS2 to receive oral doses of upadacitinib 30 mg QD at Baseline.

#### • SS1:

- Subjects randomized to enter the SS1 at Baseline will receive oral doses of upadacitinib 15 mg QD during the 12-week double-blind period.
- At Week 12, subjects from SS1 receiving upadacitinib 15 mg QD will be reassigned based on their EASI response, which is calculated based on the observed EASI value regardless of use of rescue medications:
  - Subjects achieving a < 90% reduction in EASI (< EASI 90) will be allocated to receive oral doses of upadacitinib 30 mg QD. This constitutes the Study Cohort 1 (SC1).
  - Subjects achieving a ≥ 90% reduction in EASI (≥ EASI 90) will continue to receive oral doses of upadacitinib 15 mg QD. This constitutes the Study Cohort 2 (SC2).

[figure not shown]
#### • SS2:

- Subjects randomized to enter SS2 at Baseline will receive oral doses of upadacitinib 30 mg QD during the 12-week double-blind period.
- At Week 12, subjects from SS2 receiving upadacitinib 30 mg QD will be reassigned based on their EASI response, which is calculated based on the observed EASI value regardless of use of rescue medications:
  - Subjects achieving < EASI 90 will continue to receive oral doses of upadacitinib 30 mg QD. This constitutes the Study Cohort 3 (SC3).
  - Subjects achieving ≥ EASI 90 will be allocated to receive oral doses of upadacitinib 15 mg QD. This constitutes the Study Cohort 4 (SC4).

The final and only database lock will occur at the end of the study.

The schematic of the study is shown in Figure 1.

Figure 1. Study Schematic

EASI = Eczema Area and Severity Index; QD = once daily; SS1 = Sub-Study 1; SS2 = Sub-Study 2; SC1 = Study Cohort 1; SC2 = Study Cohort 2; SC3 = Study Cohort 3; SC4 = Study Cohort 4

[figure not shown]
Note: The study will be stratified by Baseline vIGA-AD categories (3; 4) and prior use of dupilumab (yes; no).

### 2.3 Treatment Assignment and Blinding

All subjects will be assigned a unique identification number by the IRT at the screening visit. For subjects who rescreen, the screening number assigned by the IRT at the initial screening visit should be used. The IRT will assign a randomization number that will encode the subject's treatment group assignment according to the randomization schedule generated by the statistics department at AbbVie. Subjects in the study will be randomized in a 1:1 ratio to one of the 2 treatment groups:

- Upadacitinib 15 mg QD
- Upadacitinib 30 mg QD

The study will be stratified by Baseline vIGA-AD categories (3; 4) and prior use of dupilumab (yes; no).

During the 12-week double-blind period, study sites and subjects will remain blinded. During the single blind period, only the subjects will be blinded to the upadacitinib dose and the EASI score evaluations.

#### 2.4 Sample Size Determination

By Assuming:

- In SS1, 54% of subjects would be EASI 90 non-responder at Week 12.
- In SS2, 65% of the subjects would be EASI 90 responder at Week 12.
- There would be no more than 8% dropouts every 12 weeks.

A total sample size of 454 subjects will result in at least 96 subjects in SC1 and SC4, to ensure the half width of 95% CI will be within 10% for EASI 90 response estimation at Week 24.

# 3.0 Endpoints

# 3.1 Primary Endpoint

[figure not shown]
The primary endpoint is:

• Achievement of EASI 90 at Week 24.

# 3.2 Secondary Endpoints

The secondary endpoints are:

- Achievement of EASI 75/100 at Week 24.
- Achievement of EASI 75/90/100 at Week 12.
- Achievement of EASI 90 and a Worst Pruritus NRS of 0 or 1 for subjects with Worst Pruritus NRS > 1 at Baseline at Week 12 and Week 24.
- Achievement of vIGA-AD of 0 or 1 at Week 12.
- Achievement of vIGA-AD of 0 or 1 at Week 24

[figure not shown]

- Achievement of an improvement (reduction) in Worst Pruritus NRS  $\geq$  4 for subjects with Worst Pruritus NRS  $\geq$  4 at Baseline at Week 12.
- Achievement of an improvement (reduction) in Worst Pruritus NRS  $\geq$  4 for subjects with Worst Pruritus NRS  $\geq$  4 at Baseline at Week 24.
- Achievement of Worst Pruritus NRS of 0 or 1 for subjects with Worst Pruritus NRS > 1 at Baseline at Week 12.
- Achievement of Worst Pruritus NRS of 0 or 1 for subjects with Worst Pruritus NRS > 1 at Baseline at Week 24.
- Achievement of an improvement (reduction) from Baseline in DLQI ≥ 4 for subjects with DLQI ≥ 4 at Baseline at Week 12.
- Achievement of an improvement (reduction) from Baseline in DLQI ≥ 4 for subjects with DLQI ≥ 4 at Baseline at Week 24.
- Achievement of DLQI 0/1 for subjects with DLQI > 1 at Baseline at Week 12.
- Achievement of DLQI 0/1 for subjects with DLQI > 1 at Baseline at Week 24.

[figure not shown]
# 3.3 Additional Efficacy Endpoints

All variables listed as primary or secondary endpoints will be analyzed at all applicable visits other than those listed above. In addition, the following endpoints will be evaluated at all applicable visits unless otherwise specified. Additional Efficacy Endpoints are:

- Experience of a loss of response after Week 12 until Week 24 (defined as a loss of at least 50% of the EASI improvement gained from Baseline to Week 12) among subjects who had an EASI 90 response at Week 12.
- Achievement of EASI score < 7 / < 3 / < 1.
- Achievement of Worst Pruritus NRS of 0 for subjects with Worst Pruritus NRS >0 at Baseline.
- Achievement of an improvement (reduction) in Patient Oriented Eczema
   Measure (POEM) ≥ 4 from Baseline for subjects with POEM ≥ 4 at Baseline.
- Achievement of POEM  $\leq 2$  / 0 for subjects with POEM > 2 / > 0 at Baseline, respectively.

- Achievement of POEM Itch item score of 0 for subjects with POEM Itch item score >0 at Baseline.
- Achievement of POEM Sleep item score of 0 for subjects with POEM Sleep item score > 0 at Baseline.
- Change and percent change from Baseline in Patient Global Impression of Severity (PGIS).
- Achievement of "Minimal" or "Absent" on the PGIS for subjects who are "Mild" or worse on the PGIS at Baseline.
- Achievement of "Absent" on the PGIS for subjects who are "Minimal" or worse on the PGIS at Baseline.
- Change and percent change from Baseline in Patient Global Impression of Treatment (PGIT).
- Achievement of "Extremely satisfied" or "Very satisfied" on the PGIT for subjects who are "Somewhat satisfied" or worse on the PGIT at Baseline.
- Achievement of "Extremely Satisfied" on the PGIT for subjects who are "Very satisfied" or worse on the PGIT at Baseline.
- Achievement of an improvement (reduction) in Atopic Dermatitis Impact
   Scale (ADerm-IS) Sleep ≥ 12 from Baseline for subjects with ADerm-IS Sleep
   > 12 at Baseline.
- Achievement of an improvement (reduction) in ADerm-IS Emotional State
   ≥ 11 from Baseline for subjects with ADerm-IS Emotional State ≥ 11 at
   Baseline.
- Achievement of an improvement (reduction) in ADerm-IS Daily Activities
   ≥ 14 from Baseline for subjects with ADerm-IS Daily Activities ≥ 14 at
   Baseline.
- Achievement of ADerm-IS Sleep  $\leq 3$  / 0 for subjects with ADerm-IS Sleep > 3/> 0 at Baseline, respectively.
- Achievement of ADerm-IS Daily Activities  $\leq 2$  / 0 for subjects with ADerm-IS Daily Activities > 2/> 0 at Baseline, respectively.
- Achievement of ADerm-IS Emotional State  $\leq 2$  / 0 for subjects with ADerm-IS Emotional State  $\geq 2/> 0$  at Baseline, respectively.

[figure not shown]

- Achievement of an improvement (reduction) in Atopic Dermatitis Symptom Scale (ADerm-SS) Skin Pain ≥ 4 from Baseline for subjects with ADerm-SS Skin Pain ≥ 4 at Baseline.
- Achievement of ADerm-SS Skin Pain  $\leq 1$  / 0 for subjects with ADerm-SS Skin Pain  $\geq 1/>0$  at Baseline, respectively.
- Achievement of an improvement (reduction) in ADerm-SS 7-item total symptom score (TSS-7) ≥ 28 from Baseline for subjects with ADerm-SS TSS-7 ≥ 28 at Baseline.
- Achievement of ADerm-SS TSS- $7 \le 11 / \le 1$  for subjects with ADerm-SS TSS-7 > 11 / > 1 at Baseline, respectively.
- Achievement of EASI 75 / 90, for subjects who experienced an inadequate response to previous treatment with dupilumab for AD as reported by the investigator
- Achievement of EASI 90 and a Worst Pruritus NRS of 0 or 1, for subjects with Worst Pruritus NRS > 1 at Baseline and experienced an inadequate response to previous treatment with dupilumab for AD as reported by the investigator.
- Achievement of EASI 75 / 90, for subjects who were previously treated with dupilumab for AD.
- Achievement of EASI 90 and a Worst Pruritus NRS of 0 or 1, for subjects with Worst Pruritus NRS > 1 at Baseline and were previously treated with dupilumab for AD.
- For subjects participating in the Wearable Tool Substudy:
  - Change from Baseline in average nightly nocturnal scratch: total scratch time and number of scratch events.
  - Change from Baseline in the following sleep parameters: total sleep time, wake after sleep onset, sleep efficiency, and sleep onset latency.

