3.4 Additional Efficacy Endpoints

All variables listed as primary or secondary endpoints will be analyzed at all applicable visits other than those listed above. In addition, the following endpoints will be evaluated at all applicable visits unless otherwise specified.

Additional Efficacy Endpoints are:

- Experience of a loss of response after Week 12 until Week 24 (defined as a loss of at least 50% of the EASI improvement gained from Baseline to Week 12) among subjects who had an EASI 90 response at Week 12.
- Achievement of EASI score < 7 / < 3 / < 1.
- Achievement of Worst Pruritus NRS of 0 for subjects with Worst Pruritus NRS >0 at Baseline.
- Achievement of an improvement (reduction) in Patient Oriented Eczema Measure (POEM) ≥ 4 from Baseline for subjects with POEM ≥ 4 at Baseline.
- Achievement of POEM ≤ 2 / = 0 for subjects with POEM > 2 / > 0 at Baseline, respectively.
- Achievement of POEM Itch item score of 0 for subjects with POEM Itch item score >0 at Baseline.
- Achievement of POEM Sleep item score of 0 for subjects with POEM Sleep item score > 0 at Baseline.
- Change and percent change from Baseline in Patient Global Impression of Severity (PGIS).
- Achievement of "Minimal" or "Absent" on the PGIS for subjects who are "Mild" or worse on the PGIS at Baseline.
- Achievement of "Absent" on the PGIS for subjects who are "Minimal" or worse on the PGIS at Baseline.
- Change and percent change from Baseline in Patient Global Impression of Treatment (PGIT).
- Achievement of "Extremely satisfied" or "Very satisfied" on the PGIT for subjects who are "Somewhat satisfied" or worse on the PGIT at Baseline.

- Achievement of "Extremely Satisfied" on the PGIT for subjects who are "Very satisfied" or worse
 on the PGIT at Baseline.
- Achievement of an improvement (reduction) in Atopic Dermatitis Impact Scale (ADerm-IS) Sleep
 ≥ 12 from Baseline for subjects with ADerm-IS Sleep ≥ 12 at Baseline.
- Achievement of an improvement (reduction) in ADerm-IS Emotional State ≥ 11 from Baseline for subjects with ADerm-IS Emotional State ≥ 11 at Baseline.
- Achievement of an improvement (reduction) in ADerm-IS Daily Activities ≥ 14 from Baseline for subjects with ADerm-IS Daily Activities ≥ 14 at Baseline.
- Achievement of ADerm-IS Sleep ≤ 3 / = 0 for subjects with ADerm-IS Sleep > 3/> 0 at Baseline, respectively.
- Achievement of ADerm-IS Daily Activities ≤ 2 /= 0 for subjects with ADerm-IS Daily Activities
 > 2/> 0 at Baseline, respectively.

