# 9.2 Handling of Missing Data

All efficacy endpoints will be analyzed using AO approach:

• The **AO analysis** will not impute values for missing evaluations, and thus a subject who does not have an evaluation at a scheduled visit will not be included in the AO analysis for that visit.

Another missing data handling method performed as a sensitivity analysis for the primary endpoint only is Multiple Imputation (MI) approach, which defined as below:

• MI approach: Markov Chain Monte Carlo (MCMC) will be first applied to augment data into monotonic missing pattern and PROC MI will be used to generate 30 datasets using the regression method. The imputation is done in two steps for the primary endpoint.

Step 1: Missing EASI scores will be imputed. The variables to be included in the imputation model are treatment groups, actual stratification factors (vIGA-AD categories (3; 4) and prior use of dupilumab (yes; no)), baseline, and measurements at each visit. The random seed for MCMC and the random seed for PROC MI are set as 1005 and 9015. The imputed post-baseline measurements will be rounded to the same precision as the observed data before the determination of responder status.

Step 2: After obtaining the EASI 90 at Week 24 based on MI imputed values, subjects will be characterized as responders or non-responders based on MI imputed datasets. The primary endpoint will be analyzed using each of the 30 datasets. SAS PROC MIANALYZE will be used to generate the final inferences of the EASI 90 percentages, the standard errors as well as 95% CIs.

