# 9.5 Additional Efficacy Endpoints and Analyses

The additional efficacy endpoints listed in Section 3.3 will be analyzed as below. The categorical endpoints will be summarized by ITT 1 and ITT 2 populations using the AO approach. For the categorical endpoints, counts and percentages will be provided along with 95% CIs, by visit and by treatment group. For the continuous endpoints, Least Square (LS) mean, 95% CI and standard error (SE) will be provided using ANCOVA including treatment, baseline, stratification factors (vIGA-AD categories [3; 4] and prior use of dupilumab [yes; no]) in the model.

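### Percent change from Baseline in PGIS and PGIT depends on how the verbal categories are numbered, so it should be dropped in favour of change and category summaries

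*SAP*

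**What the plan says.** Protocol Section 3.4 lists "Change and percent change from Baseline in Patient Global Impression of Severity (PGIS", and the same pair for PGIT. SAP Section 3.3 repeats both, the PGIT entry reading "Change and percent change from Baseline in Patient Global Impression of Treatment (PGIT".

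The same lists show what kind of scales these are. The responder endpoints are worded by category: "Achievement of 'Minimal' or 'Absent' on the PGIS for subjects who are 'Mild' or worse on the PGIS at Baseline" and "Achievement of 'Extremely satisfied' or 'Very satisfied' on the PGIT for subjects who are 'Somewhat satisfied' or worse on the PGIT at Baseline". Neither document gives numeric codes, their direction, or the number of levels.

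SAP Section 9.5 sets the method: "For the continuous endpoints, Least Square (LS) mean, 95% CI and standard error (SE) will be provided using ANCOVA", with treatment, Baseline and the stratification factors in the model. SAP Table 2 gives the same model for continuous variables in both periods. On missing data, SAP Section 9.2 says "The AO analysis will not impute values for missing evaluations". Neither document says what to do when the Baseline value in a percent change is zero.

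**The concern.** Percent change is a ratio to the Baseline value, so it has a stable meaning only if zero on the scale means none of the thing measured. One can argue that *Absent* on PGIS is such a zero. Satisfaction with treatment has no natural zero, so the number attached to the lowest PGIT category is a convention.

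Mean change is less exposed. Adding a constant to every code leaves it alone, and reversing the scale only flips its sign. Mean percent change can alter in size under either operation.

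The study is descriptive, and patient-reported impact is a stated additional objective (SAP Section 2.1), so the printed estimates are the product. A least-squares mean percent change with a 95% CI looks precise and invites comparison across the 15/15, 15/30, 30/15 and 30/30 groups of SAP Table 1. If Baseline distributions differ between those groups, which are formed by Week 12 response, part of any contrast may reflect the code origin.

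In both documents, PGIS and PGIT are the only listed efficacy endpoints given percent change from Baseline. The wearable measures of scratch time, scratch events and total sleep time, which do have a true zero, get change only.

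**Working it through.** **Inputs.** The plan states no PGIS or PGIT figure, so there is nothing to reproduce. From the documents: the endpoint definitions, the verbal categories, the ANCOVA summary and the as-observed rule. Assumed, because the documents do not give it: seven equally spaced levels, coded 1 to 7, 0 to 6, or -3 to +3, in either direction.

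**Formula.** Percent change = 100 × (post - base) / base. If one subject moves from code a to code b and another from b to a, mean change is 0 and

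mean percent change = 50 × [(b - a)/a + (a - b)/b] = 100 × (b - a)² / (2ab).

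The numerator does not depend on the origin of the codes. The denominator does.

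**Check 1: origin.** Two subjects swap between levels 2 and 6. Mean change is 0 in every row.

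| Coding | Codes | Individual percent changes | Mean |
|---|---|---|---|
| 1 to 7 | 2 and 6 | +200, -66.7 | +66.7% |
| 0 to 6 | 1 and 5 | +400, -80 | +160% |
| -3 to +3 | -2 and +2 | -200, -200 | -200% |

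With 1 to 7 reversed the result is again +66.7%, but it now reads as worsening, because higher codes are worse.

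**Check 2: direction.** Four subjects improve from levels 1, 2, 3 and 4 to level 6.

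- Coded 1 to 7 with 7 best: +500, +200, +100, +50. Mean 850/4 = +212.5%; median (200 + 100)/2 = +150%.
- Coded 1 to 7 with 1 best (7, 6, 5, 4 to 2): -71.4, -66.7, -60, -50. Mean -248.1/4 = -62.0%; median (-66.7 - 60)/2 = -63.3%.
- Mean change is (5 + 4 + 3 + 2)/4 = 3.5 categories in both, with opposite sign.

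**Check 3: ranking.** A move from 4 to 2 and a move from 6 to 3 are both -50%. Add 1 to every code and they become -2/5 = -40% and -3/7 = -42.9%. A tie turns into a difference although no subject's category has changed.

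**Check 4: small moves.** A one-step swap between codes 3 and 4 gives 100 × 1/(2 × 3 × 4) = +4.2%. Between codes 1 and 2 it gives 100 × 1/(2 × 1 × 2) = +25%. At middle codes the effect is a few percent.

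**Check 5: zero code, conditional.** Coded 0 to 6 with 6 best, the four subjects of Check 2 go from 0, 1, 2, 3 to 5. The first value is 5/0, undefined. If that subject is left out, the others give (400 + 150 + 66.7)/3 = +205.6%.

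**Does ANCOVA repair this?** No. Adjusting for Baseline does not change the quantity being averaged. In a single group with Baseline as covariate, the least-squares mean at the mean Baseline equals the raw mean.

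**The case against.** **The coding may be fixed elsewhere.** The Operations Manual, which may hold it, is not among the documents reviewed. Once a coding is fixed the result is reproducible. That stands: a reader might infer that the planned numbers would be meaningless, but the documents support only that they depend on an unstated convention. Fixing it makes the figure repeatable; it does not give PGIT a natural zero.

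**Zero codes and lost subjects.** A reader might infer that subjects will be lost through zero Baseline codes, or that the as-observed rule removes them. The documents support neither. No code is given, and with codes from 1 nothing is undefined. For PGIS with 0 as *Absent*, a Baseline zero should be rare, because entry requires EASI of at least 16, vIGA-AD of at least 3 and a weekly Worst Pruritus NRS of at least 4 (protocol Section 5.1). The case that could matter is a worst PGIT category coded 0. The as-observed rule covers missing evaluations, not an undefined ratio; the plan has no rule for the latter.

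**The asymmetry is not special to categories.** This is correct. Opposite moves fail to cancel in percent terms on any scale, including true ratio scales. What is particular here is that the size depends on an arbitrary origin.

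**Low codes need not dominate the mean.** Also correct. In Check 2 one subject supplies 500 of 850 points under one direction and nothing comparable happens under the other. SAP Section 9.1 also plans medians and ranges, which would reveal skew, although the median depends on the coding too.

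**Mean change also assumes equal steps.** True, and a reason to add the category distribution. Mean change still escapes the dependence on origin.

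**Stakes are low.** The SAP states "No hypothesis testing will be performed in this study", and no primary or secondary endpoint uses PGIS or PGIT.

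**Conclusion.** The point holds as a minor one. The plan would report mean percent changes whose size depends on the origin and direction of a numbering that neither document states. Under the assumed seven-level scale, one pair of opposite moves gives +67%, +160% or -200% with mean change 0 throughout. That is a deliberately large move; for a one-step swap at codes 3 and 4 the effect is about 4%. The exact sizes rest on the assumed number of levels and codes. The dependence itself follows from dividing by the Baseline code.

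The argument is stronger for PGIT than for PGIS, whose lowest category could serve as a zero. The undefined-value problem arises only if some Baseline category is coded 0. The effect is confined to additional descriptive endpoints; primary and secondary results, and the responder endpoints on these two scales, are unaffected.

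**What to change.** - In SAP Section 3.3, delete percent change for PGIS and PGIT.
- Record the departure from protocol Section 3.4 in SAP Section 14.1, which now reads as not applicable. The protocol wording can follow at the next amendment. An amendment for this alone is not warranted, since protocol Section 8.1 requires ethics review of any amendment.
- Keep the planned change from Baseline and the category responder endpoints.
- State the numeric coding and direction of both scales in the SAP.
- Add the distribution over categories by visit and treatment group, which needs no assumption about equal steps.

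The cost is a small SAP edit, one distribution table per scale in place of the percent-change tables, and one small departure from the protocol's endpoint list. No new data are needed.
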